The AK lesions may cause cosmetic discomfort and due to the premalignant nature of the condition, patients may fear developing skin cancer. This fear may affect patients' overall well-being by leading to anxiety and stress (Tennvall et al, 2015). Patients may feel embarrassed and frustrated with AK lesions located on the face (Esmann et al, 2007). Studies have shown that AK has negative impact on the patient's daily living activities and their Quality of Life (QoL) (Grada et al, 2021), and presence of higher AK lesion counts on the face have been shown to be associated with worse skin-related quality of life among AK patients (Siegel et al, 2017; Emilio et al, 2016). AK treatments are associated with different levels of local skin reactions (LSRs) such as erythema, swelling, erosion, crusts, scaling, itching and burning sensation (Jansen et al, 2019), and such negative experiences with treatment may adversely impact the future willingness to retreat and treatment adherence among AK patients that can lead to poor outcomes in long term (Balcer et al, 2019; Del Rosso et al, 2014; Goldberg, 2017; Rosso et al., 2021). Therefore,

it is important to incorporate PROs that provides patient perspectives and provides important supplement to efficacy and safety data for the treatment(s), showcasing their complete value proposition.

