3 OBJECTIVES

3.1 Study Objectives

The primary objective of the study is to evaluate PROs in terms of health-related quality of life (HRQoL) among Subjects with AK in the face or scalp who are administered tirbanibulin in real-world community practice settings in the U.S. The secondary objective is to evaluate effectiveness of tirbanibulin treatment, measured by Investigator Global Assessment (IGA) of the status of AK in the treated area on the face or scalp.

The additional study objectives include the following evaluations among study Subjects and Site Investigators:

- Subject and clinician satisfaction with tirbanibulin treatment and associated outcomes.
- Subject and clinician reported improvement in overall appearance of Subject's skin in the treated area.
- Subject and clinician reported effect/impact of LSRs.
- Subject and clinician reported future treatment preference.
- Safety and tolerability of tirbanibulin.

Note: Dermatologists are expected to predominantly constitute the Site Investigator category, while a few physician assistants and nurse practitioners may be included in the study, reflecting the routine care management of AK in community practice settings.

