6.1 Sample Size Considerations

No formal sample size and power calculations were undertaken. Considering the descriptive nature of the study and the feasibility of recruiting the study population, approximately 300 study Subjects from across a maximum of 50 clinical sites for the entire study has been identified as a sample to guide the planned analysis addressing the study objectives.

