6.6.8 Prior and Concomitant Medications

Medication usage is coded using the latest (2022) WHO Drug Dictionary. Medications are presented by WHO Drug Anatomical/Therapeutic/Chemical (ATC) category and WHO Drug preferred name. Summaries are presented for prior (prior to the first dose of study treatment, gathered as aggregate indicators as well as at individual item level) medication use and concomitant (after first dose of study treatment had been given, gathered at individual item level) medication use. Medications with an end date occurring before the first study treatment (tirbanibulin) date in the treatment period are identified as prior medications. Medications with a start date occurring on or after the first study treatment (tirbanibulin) date in the treatment period or medications with a start date prior to the first (tirbanibulin) dose that were ongoing or with end dates that were on or after 8 weeks post index date are identified as concomitant medications.

Concomitant AK and non-AK medications are captured at Baseline and at Week-8 to characterize the use of concomitant medications among the study cohort. Additional information is captured at Week-24 if the patient was re-treated with tirbanibulin, another topical treatment for AK, or a non-topical treatment for AK between the week-8 and week-24 timepoints.

All summaries present the number (%) of subjects for each medication. The denominators for calculating the percentages are based on the number of subjects in the FAS population.

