3 /4 Minimally/ Not Cleared	n (%)	n (%)

Table 2.11 IGA Success at Week 8 in the Original Treated Area

Character	Week 8
IGA Success	N=x
No	n (%)
Yes	n (%)

Note: IGA success at Week 8, defined as an IGA score of completely cleared (0) or partially cleared (1) in AK status in the original treated area at Week 8. The denominator for the percentages is the number of patients with available data (N=XX). X patients had missing data at Week 8.

Table 2.12 Subgroup Analysis of IGA Success

% IGA Success (Completely/Partially Cleared)		Week 8 n (%)	Week 24 n (%)
Subgroups			
Gender			
Male			
Female			
p -value			
Age Group			
≤ 49 years			
50 – 64 Years			
≥ 65 years			
p -value			
AK Treatment Location			
Face			
Scalp			
Both			
p -value			
Fitzpatrick Skin Type			
I / II			
III / IV / V / VI			
p -value			
Skin Photodamage			
Absent/mild			
Moderate/Severe			
p -value			
History of Skin Cancer			
Yes			
No			
p -value			
Prior Treatment Experience: Use of Cryosurgery			
Yes			
No			
p -value			
Prior Treatment Experience: Use of Other Topical Treatments			
Yes			
No			
p -value			

Prior Treatment Experience: Treatment Naïve at Baseline

Yes

No

p-value

P-values correspond to difference between strata within respective time periods.

Table 2.13 Clinician Evaluation of Overall Appearance in the Original Treated Area

Character	Week 8 (N=x)	Week 24 (N=X)
Compared to 8 / 24 weeks ago, how has the patient's overall appearance of the skin in the original AK treated area changed?		
1. Much Worse	AK8_2	AK8_2
2. Somewhat Worse	n (%)	n (%)
3. No Change	n (%)	n (%)
4. Somewhat improved	n (%)	n (%)
5. Much Improved	n (%)	n (%)
(1/2) Much/Somewhat Worse	n (%)	n (%)
(3) No Change	n (%)	n (%)
(4/5) Somewhat/Much Improved	n (%)	n (%)

Table 2.14 Subgroup Analysis of Clinician Evaluation of Overall Appearance in the Original Treated Area

% Somewhat / Much Improved	Week 8 n (%)	Week 24 n (%)
Subgroups		
Gender		
Male		
Female		
p -value		
Age Group		
≤ 49 years		
50 – 64 Years		
≥ 65 years		
p -value		
AK Treatment Location		
Face		
Scalp		
Both		
p -value		
Fitzpatrick Skin Type		
I / II		
III / IV / V / VI		
p -value		
Skin Photodamage		
Absent/mild		
Moderate/Severe		
p -value		
History of Skin Cancer		
Yes		
No		
p -value		
Prior Treatment Experience: Use of Cryosurgery		
Yes		
No		
p -value		
Prior Treatment Experience: Use of Other Topical Treatments		
Yes		
No		

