EPQ8A Among the list of factors that influenced your overall satisfaction with tirbanibulin (Klisyri®), please identify the three most important factors and rank them on a scale of importance from 1 to 3, where 1 is the first most important factor, 2 is the second most important factor and 3 is the third most important factor to you, by entering a number in the boxes next to only those factors in the following list.

Domain	Rank 1	Rank 2	Rank 3	Average Rank
[EPQ8Ar1] Product convenience: Length of treatment, frequency, and easiness to take, etc. (N=x)	n (%)	n (%)	n (%)	
[EPQ8Ar2] Product effectiveness: Impact on skin appearance. (N=x)	n (%)	n (%)	n (%)	
[EPQ8Ar3] Product effectiveness: Impact on AK lesion clearance. (N=x)	n (%)	n (%)	n (%)	
[EPQ8Ar4] Product effectiveness: Amount of time it takes to start working. (N=x)	n (%)	n (%)	n (%)	
[EPQ8Ar5] Product side-effects: Amount of time it takes for local skin reactions to resolve. (N=x)	n (%)	n (%)	n (%)	
[EPQ8Ar6] Product side-effects: Number and type of local skin reactions. (N=x)	n (%)	n (%)	n (%)	
[EPQ8Ar7] Product side-effects: Severity of the local skin reactions. (N=x)	n (%)	n (%)	n (%)	
[EPQ8Ar8] Product tolerability: Ability to adhere to treatment dose, or intensity. (N=x)	n (%)	n (%)	n (%)	
[EPQ8Ar9] Other: (N=x) EPQ8Ar9oe	n (%)	n (%)	n (%)	

Table 2.29 Unscheduled Patient Encounters Reported at Week 8

Domain	Week 8 (N=x)
[US1_1r1] Number of unscheduled in-person clinic visits:	n (%)
[US1_1r2] Number of unscheduled tele-health visits:	n (%)
[US1_1r3] Number of unscheduled phone calls:	n (%)

Table 2.30 Prior AK Treatment (To-Date) Including within the Past 6 Months

Character TH2 and TH3 (Start date prior to Klisyri®; End date within the past 6 months or No end date)	Baseline (N=x)
TH2A checked AND TH3=No Has not use any AK medication	n (%)
Topical medication	
[TH2r1] 5-Fluorouracil (5-FU)	
[TH2r2] Salicylic acid	
[TH2r3] Imiquimod	
[TH2r4] Ingenol mebutate	n (%)
[TH2r5] Diclofenac	
[TH2r6] Other [TH2r6oe]	
A	
B	
C	
Oral medication:	
[TH2r7] Isotretinoin	
Other	
A	n (%)
B	
C	
Other therapies:	
[TH2r8] Photodynamic therapy	
[TH2r9] Cryosurgery/Cryotherapy	
[TH2r10] Chemical/acid peel	
[TH2r11] Curettage	
[TH2r12] Laser therapy	n (%)
Other:	
A	
B	
C	

Note: Data from Clinician DCF; X patients had missing data; The denominator for the percentages is the number of patients with available data (N=X)

Table 2.31 AK Concomitant Medication Use During the 8-Week Observation Period

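### Other AK therapy between index and Week 8 is recorded but never used in Week-8 IGA success or Skindex-16 change, so clearance it produces in the treated area counts as tirbanibulin effectiveness

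*SAP*

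**What the plan says.** Protocol 3.1 ties the IGA to the drug: "The secondary objective is to evaluate effectiveness of tirbanibulin treatment". The design is single-arm (Protocol 4, SAP 3). The protocol summary leaves patient management to usual clinical practice, and neither eligibility list (Protocol 6.1 and 6.2, SAP 3.1 and 3.2) sets a washout or a limit on other AK therapy. No sentence expressly allows such therapy; permission follows from the absence of any restriction.

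The therapy is recorded. SAP 6.6.8 states: "Concomitant AK and non-AK medications are captured at Baseline and at Week-8 to characterize the use of concomitant medications among the study cohort". Table 2.31, "AK Concomitant Medication Use During the 8-Week Observation Period", has lines for topical agents, photodynamic therapy, cryosurgery, peel, curettage and laser. Table 2.30 covers earlier therapy with "End date within the past 6 months or No end date".

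The endpoints do not refer to it. Table 2.11 gives "IGA success at Week 8, defined as an IGA score of completely cleared (0) or partially cleared (1", with all patients who have data in the denominator. Skindex-16 change (SAP 6.4, Table 1.8) is a plain descriptive change in the FAS. The sensitivity analyses (SAP 6.9 and 7.5) concern missing data and visit type.

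**The concern.** A patient whose remaining lesions in the treated area are treated by another method before the Week-8 rating, and who is then rated 0 or 1, is reported as a success in a table meant to describe tirbanibulin's effectiveness. No control arm carries the same co-treatment.

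The plan recognises the issue after Week 8. SAP 6.3.3 considers subgroups by type of retreatment, and Table 2.36 asks whether retreatment was aimed at the original lesions. Nothing comparable exists for the window that determines the primary and secondary endpoints.

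The primary endpoint may be touched as well. Protocol 2.1 associates AK treatments with "local skin reactions (LSRs) such as erythema, swelling, erosion, crusts, scaling, itching and burning sensation". Skindex-16 items 1 and 2 ask about itching and about burning or stinging over the past week. A reaction to another therapy, at baseline or at Week 8, would therefore enter the Symptoms score.

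**Working it through.** **Inputs.** SAP 6.1 gives the planned size: "approximately 300 study Subjects from across a maximum of 50 clinical sites for the entire study has been identified as a sample". It also says "No formal sample size and power calculations were undertaken", so the plan has no figure of its own to reproduce. The documents give no rate of other AK therapy and no expected IGA success rate. Every rate below is an assumption, used for scale only.

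**Formula for IGA success.** Let c be the share with other AK therapy in the treated area by the Week-8 rating, s their observed success rate, p the success rate they would have had without the add-on, and p0 the rate in everyone else.

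- As observed: (1 − c) × p0 + c × s
- Without the add-on: (1 − c) × p0 + c × p
- Bias: the difference, c × (s − p)
- Co-treated counted as non-successes: (1 − c) × p0, which lies c × s below the observed rate
- Co-treated excluded: p0

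Since p cannot be below zero, c × s is the upper bound on the bias. The count-as-non-success row amounts to p = 0 and the exclusion row to p = p0. If p lies between 0 and p0, the two rows bracket the rate without the add-on.

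**Numbers,** with s = 90% and p = p0 = 60%:

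| c | Patients of 300 | As observed | Bias c × (s − p) | Counted as non-success | Upper bound c × s | Excluded |
|---|---|---|---|---|---|---|
| 2% | 6 | 60.6% | 0.6 points | 58.8% | 1.8 points | 60.0% |
| 10% | 30 | 63.0% | 3.0 points | 54.0% | 9.0 points | 60.0% |
| 20% | 60 | 66.0% | 6.0 points | 48.0% | 18.0 points | 60.0% |

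Across p = p0 from 50% to 70% and s from p up to 100%, the largest bias is 0.02 × (100 − 50) = 1 point at c = 2%, 0.10 × 50 = 5 points at 10% and 0.20 × 50 = 10 points at 20%. The smallest is 0. If co-treated patients do worse than they would have without the add-on, the sign reverses: c = 3%, s = 50% and p = 60% give 0.03 × (50 − 60) = −0.3 points.

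**Comparison with sampling error.** The 95% half-width, 1.96 × √(p(1 − p)/300), is 5.7 points at 50% and 5.2 points at 70%. At 10% use, the largest bias in this range is about the size of the sampling error. At 20% use it can exceed it. At 2% it is well below.

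**Skindex-16.** If a share c of patients carries d extra points from another therapy's reaction, the mean change shifts by c × d. For d between 5 and 20 (assumed), this runs from 0.02 × 5 = 0.1 to 0.20 × 20 = 4 points. Extra points at baseline inflate the improvement; extra points at Week 8 reduce it.

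**Which therapies count.** Under SAP 6.6.8, a medication is prior if it ended before the first dose. It is concomitant if it started on or after the first dose, or if it started earlier and was ongoing or ended at or after 8 weeks. A therapy started before index and stopped between index and Week 8 is neither. Table 2.31 appears to include it, because its condition is an end date after the Klisyri start and within the 8 weeks.

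**The case against.** In a descriptive usual-care cohort, the as-observed rate is a legitimate headline, and Table 2.31 would let a reader see how common co-treatment was. That stands, and is why the headline should not change. It does not tell the reader how many of the successes were co-treated.

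Carry-over from earlier therapy is partly limited. Protocol 6.1 requires visible lesions at entry. Protocol 6.2 excludes open wounds near the treatment area and skin conditions that would interfere with evaluation. Protocol 7.3 has the IGA rated against baseline, so lesions already gone earn no credit; only lesions still regressing could. The treatment-naive stratum in Tables 1.9 and 2.12 is free of prior-therapy carry-over, although SAP 6.3.3 makes it optional. These points stand, but none of them concerns therapy given after index. The adjusted models of Protocol 12.3.4 are conditional on feasibility, do not name other AK therapy and have no counterpart in the SAP.

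A reader might infer that the plan expects substantial co-treatment, or that it would go mainly to patients with residual lesions. The documents support neither. Table 2.31 largely repeats the therapy list of Table 2.30 and shows that data are captured, not that use is expected. Apart from the photography sites (at most two), no visit is scheduled between baseline and Week 8.

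**Conclusion.** The gap is real and modest. Other AK therapy in the 8-week window is unrestricted and recorded, yet plays no part in the IGA or Skindex-16 results, while the stated objective attributes the IGA to tirbanibulin. On the assumed s = 90% and p = 60%, the bias in IGA success is about 0.6 points at 2% use, 3 at 10% and 6 at 20%. It may be negligible if use is rare.

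Two stronger readings are tempting. One takes c × s as the overstatement; that would require every co-treated patient to have failed on tirbanibulin alone, which nothing in the documents shows. The other holds that the Skindex-16 error also favours the drug. With a one-week recall, a reaction to add-on therapy shortly before Week 8 would count against it, so the direction is uncertain.

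**What to change.** Patient care and the as-observed headline stay as they are; only the reporting changes.

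1. In Table 2.11, add two supportive rows for patients with lesion- or field-directed AK therapy listed in Table 2.31 between index and the Week-8 rating: one counting them as non-successes, one excluding them. Limit both to therapy in the treated area where the records show this.
2. Repeat Table 1.8 without these patients. As a further check, repeat it without patients whose other AK therapy was ongoing at index or ended shortly before it. Fix the cut-off before analysis and show the treatment-naive stratum alongside.
3. Reconcile the concomitant definition in SAP 6.6.8 with Table 2.31, so that therapy started before index and stopped before Week 8 has one defined place.

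A data item for whether the therapy was in the treated area would help but is optional. The SAP appears to have been written after enrolment, so it would probably be completed retrospectively.

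The cost is SAP wording and a few table rows from therapy data already collected. The count-as-non-success rate will be equal to or lower than the headline, and the restricted displays will have fewer patients.

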Table 2.35 Patient Treatment Details, If Retreated After Week 8: Clinician Reported

Domain	Week 24 (N=x)
RMH2: I started a new AK treatment for this patient within the past 16 weeks, following patient's Week-8 visit.	
RHM2 = 2 No	n (%)
RMH2Ar1: Tirbanibulin (Klisyri®)	n (%)
RMH2Ar2: Another topical treatment	n (%)
A [OTE1r1]	
RMH2Ar3: Another treatment (which is not topical)	n (%)
A [NTR1r1]	

Note: Data from Clinician DCF, from week-24.

Table 2.36 Reason for Retreatment, If Retreated with After Week 8

Domain	Statistics	Week 24			Total
		Retreated with Klisyri® (RMH2Ar1) (N=x)	Retreated with Another Topical Treatment (RMH2Ar2) (N=x)	Retreated with Non-Topical Treatment (RMH2Ar3) (N=X)	
Why was this patient re-treated?					
1. To manage newly emerged AK lesions	n (%)	RTE1_5r1	OTE1r7r1	NTR1r7r1	
2. To re-treat original* treated AK lesions	n (%)	RTE1_5r2	OTE1r7r2	NTR1r7r2	
3. Other	n (%)	[RTE1_5r3oe]	[OTE1r7r3oe]	[NTRr7r3oe]	

Note: Data from Clinician DCF, from week-24.

Table 2.37 Area of Tirbanibulin Treatment, If Retreated with After Week-8

Character	Week 24 If retreated with Klisyri® (N=x)
AK3A1: What is the AK treatment area you have identified for the patient, to apply tirbanibulin (Klisyri®)?	
Left	
Face	n (%)
Scalp	n (%)
Right	
Face	n (%)
Scalp	n (%)
Center	
Face	n (%)
Scalp	n (%)
Unknown	
Face	n (%)
Scalp	n (%)
Overall	
Face (any area)	n (%)
Scalp (any area)	n (%)

Note: Data from Clinician DCF, from week-24.

Table 2.38 Tirbanibulin Treatment Characteristics if Retreated after Week 8

Character	Week 24 If retreated with Klisyri® (N=x)
TH1B: Prescription dose	
1. 1% tirabibanibulin, single-dose packets	n (%)
2. Other, please specify [TH1Br2oe]	n (%)
a. X	
TH1C: Prescription frequency	
1. Once daily for 5 consecutive days	n (%)
2. Other, please specify: [TH1Cr2oe]	n (%)
a. X	
RTE1_4: Treatment Status	
1. Patient completed the planned treatment course	n (%)
2. Discontinued due to treatment side-effect	n (%)
3. Discontinued due to treatment intolerance	n (%)
4. Discontinued due to lack of effectiveness	n (%)
5. Discontinued due to other reasons: [RTE1_4r5oe]	n (%)
6. Don't know / Not applicable	n (%)
RTE1_5: Why was this patient re-treated	
RTE1_5r1: To manage newly emerged AK lesions	n (%)
RTE1_5r2: To re-treat original* treated AK lesions	n (%)
RTE1_5r3: Other reason: [RTE1_5r3oe]	n (%)

Note: Data from Clinician DCF, from week-24.

Table 2.39 Treatment Satisfaction Questionnaire for Medication: Clinician Scores, If Retreated with Tirbanibulin after Week 8

Domain	Week 24
	If retreated with Klisyri®
	N=xx
Effectiveness	Mean (SD) Median Min, Max
Convenience	Mean (SD) Median Min, Max
Global Satisfaction	Mean (SD) Median Min, Max

Note: Data from Clinician DCF, from week-24.

Instructions for TSQM Scoring:

Variables TS1 - TS9

TSQM			
Scoring Steps	Global Satisfaction Score	Effectiveness Score	Convenience Score
1	Sum TS7 TS8 TS9	Sum TS1 TS2 TS3	Sum TS4 TS5 TS6
2	Subtract 3	Subtract 3	Subtract 3
3	Divide 14	Divide 18	Divide 18
4	Multiple 100	Multiple 100	Multiple 100
	Output: Average Score per patient		

Table 2.40 Clinician Satisfaction with Tirbanibulin, If Retreated with Tirbanibulin after Week 8 (looks/texture)

Domain	Week 24 If retreated with Klisyri® (N=x)
EPQ1_2: How satisfied are you with this treatment's ability to improve how your patient's skin looks (example: reduced redness, discoloration, crusting, scaling), in the original AK treated area?	Mean (SD), Median, Min,Max
1. Extremely Dissatisfied	n (%)
2. Very Dissatisfied	n (%)
3. Dissatisfied	n (%)
4. Somewhat Satisfied	n (%)
5. Satisfied	n (%)
6. Very Satisfied	n (%)
7. Extremely Satisfied	n (%)
(1 / 2) Extremely/Very Dissatisfied	
(3 / 4 / 5) Dissatisfied/Somewhat Satisfied/Satisfied	n (%)
(6 / 7) Very/Extremely Satisfied	n (%)
	n (%)
EPQ2_2: How satisfied are you with this treatment's ability to improve your patient's skin texture (i.e., how the skin feels in terms of roughness, bumpiness, scaliness) as a result of the treatment, in the original AK treated area?	Mean (SD), Median, Min,Max
1. Extremely Dissatisfied	n (%)
2. Very Dissatisfied	n (%)
3. Dissatisfied	n (%)
4. Somewhat Satisfied	n (%)
5. Satisfied	n (%)
6. Very Satisfied	n (%)
7. Extremely Satisfied	n (%)
(1 / 2) Extremely/Very Dissatisfied	
(3 / 4 / 5) Dissatisfied/Somewhat Satisfied/Satisfied	n (%)
(6 / 7) Very/Extremely Satisfied	n (%)
	n (%)

Note: Data from Clinician DCF, from week-24.

Table 2.41 Clinician Relative Satisfaction of Tirbanibulin in Comparison with Other Topical Medications for AK, If Retreated with Another Topical Treatment after Week 8

Domain	Week 24 if retreated with another topical (N=X)
RS1: Compared to your patient's previous experience with topical treatment X for AK, how would you rate the duration of skin reactions (i.e., how long the skin reactions lasted) associated with tirbanibulin (Klisyri®) that the patient experienced in the original AK treated area?	RS1 Mean (SD), Median,Min,Max
1. Duration of skin reactions was much shorter with tirbanibulin	n (%)
2. Duration of skin reactions was somewhat shorter with tirbanibulin	n (%)
3. Duration of skin reactions was the same with tirbanibulin	n (%)
4. Duration of skin reactions was somewhat longer with tirbanibulin	n (%)
5. Duration of skin reactions was much longer with tirbanibulin	n (%)
(1 / 2) Duration of skin reactions was much / somewhat shorter with tirbanibulin	n (%)
(3) Duration of skin reactions was the same with tirbanibulin	n (%)
(4 / 5) Duration of skin reactions was somewhat / much longer with tirbanibulin	n (%)
EPQ4: Compared to your patient's previous experience with topical treatment X for AK, how would you rate the severity of skin reactions (i.e., how bad the skin reactions were) associated with tirbanibulin (Klisyri®) that the patient experienced in the original AK treated area?	RS2 Mean (SD), Median,Min,Max
1. Severity of skin reactions was much better with tirbanibulin	n (%)
2. Severity of skin reactions was somewhat better with tirbanibulin	n (%)
3. Severity of skin reactions was the same with tirbanibulin	n (%)
4. Severity of skin reactions was somewhat worse with tirbanibulin	n (%)
5. Severity of skin reactions was much worse with tirbanibulin	n (%)
(1 / 2) Severity of skin reactions was much / somewhat better with tirbanibulin	n (%)
(3) Severity of skin reactions was the same with tirbanibulin	n (%)

(4 / 5) Severity of skin reactions was much / somewhat worse with tirbanibulin	n (%)
EPQ5: Compared to your patient's previous experience with treatment X, how would you rate the impact on patient's daily activities (such as shopping, bathing, social engagements, scheduling vacations, activities at work, attendance at work, etc.) due to skin reactions associated with tirbanibulin (Klisyri®) use in the original AK treated area?	RS3 Mean (SD), Median,Min,Max
1. Much better with tirbanibulin	n (%)
2. Somewhat better with tirbanibulin	n (%)
3. Same with tirbanibulin	n (%)
4. Somewhat worse with tirbanibulin	n (%)
5. Much worse with tirbanibulin	n (%)
(1 / 2) Much / somewhat better with tirbanibulin	n (%)
(3) Same with tirbanibulin	n (%)
(4 / 5) Somewhat / much worse with tirbanibulin	n (%)
EPQ6: Compared to your patient's previous experience with topical treatment X for AK, how would you rate the convenience / ease of use (such as frequency of use, easy to follow instructions, comfortable at apply, etc.) associated with tirbanibulin (Klisyri®) treatment?	RS4 Mean (SD), Median,Min,Max
1. Ease of use & convenience was much better with tirbanibulin	n (%)
2. Ease of use & convenience was somewhat better with tirbanibulin	n (%)
3. Ease of use & convenience was the same with tirbanibulin	n (%)
4. Ease of use & convenience was somewhat worse with tirbanibulin	n (%)
5. Ease of use & convenience was much worse with tirbanibulin	n (%)
(1 / 2) Ease of use & convenience was much / somewhat better with tirbanibulin	n (%)
(3) Ease of use & convenience was the same with tirbanibulin	n (%)
(4 / 5) Ease of use & convenience was somewhat / much worse with tirbanibulin	n (%)
EPQ7: Compared to your patient's previous experience with topical treatment X for AK, how would you rate your overall satisfaction (considering the factors such as convenience/ ease of use, duration and severity of skin reactions, impact on patient's daily life, etc.) with tirbanibulin (Klisyri®) treatment?	RS5 Mean (SD), Median,Min,Max

1. My satisfaction is much better with tirbanibulin	n (%)
2. My satisfaction is somewhat better with tirbanibulin	n (%)
3. My satisfaction is same with tirbanibulin	n (%)
4. My satisfaction is somewhat worse with tirbanibulin	n (%)
5. My satisfaction is much worse with tirbanibulin	n (%)
 (1 / 2) My satisfaction is much / somewhat better with tirbanibulin	n (%)
(3) My satisfaction is same with tirbanibulin	n (%)
(4 / 5) My satisfaction is somewhat / much worse with tirbanibulin	n (%)

Note: *EPQ3 – EPQ7 only asked if patient was indicated using a topical treatment for AK prior to the start of the study. Treatment X refers to this topical treatment(s) and was piped in from the baseline clinician survey.

Note: Data from Clinician DCF, from week-24.

Table 2.42 Factors Influencing Overall Clinician Satisfaction with Tirbanibulin, If Retreated after Week 8

EPQ8 What factors influenced your response to the previous question about your overall satisfaction with tirbanibulin (Klisyri®)? **Selected**

Domain	Week-24 if retreated with another topical treatment (N=X) [RS6r1] n (%)	Week 24 If retreated with Klisyri® (N=x) [EPQ8_2r1] n (%)
Product convenience: Length of treatment, frequency, and easiness to take, etc.		
Product effectiveness: Impact on skin appearance.	[RS6r2] n (%)	[EPQ8_2r2] n (%)
Product effectiveness: Impact on AK lesion clearance.	[RS6r3] n (%)	[EPQ8_2r3] n (%)
Product effectiveness: Amount of time it takes to start working.	[RS6r4] n (%)	[EPQ8_2r4] n (%)
Product side-effects: Amount of time it takes for local skin reactions to resolve.	[RS6r5] n (%)	[EPQ8_2r5] n (%)
Product side-effects: Number and type of local skin reactions.	[RS6r6] n (%)	[EPQ8_2r6] n (%)
Product side-effects: Severity of the local skin reactions.	[RS6r7] n (%)	[EPQ8_2r7] n (%)
Product tolerability: Ability to adhere to treatment dose, or intensity.	[RS6r8] n (%)	[EPQ8_2r8] n (%)
Other:	[RS6r9] n (%)	[EPQ8_2r9] n (%)
	[RS6r9oe]	EPQ8r9oe

Note: Data from Clinician DCF, from week-24.

Table 2.43 Top-3 Factors Influencing Overall Clinician Satisfaction with Tirbanibulin at Week 24, If Retreated with Tirbanibulin after Week-8

EPQ8A Among the list of factors that influenced your overall satisfaction with tirbanibulin (Klisyri®), please identify the three most important factors and rank them on a scale of importance from 1 to 3, where 1 is the first most important factor, 2 is the second most important factor and 3 is the third most important factor to you, by entering a number in the boxes next to only those factors in the following list.

Domain	Rank 1	Rank 2	Rank 3	Average Rank
[EPQ8Ar1] Product convenience: Length of treatment, frequency, and easiness to take, etc. (N=x)	n (%)	n (%)	n (%)	
[EPQ8Ar2] Product effectiveness: Impact on skin appearance. (N=x)	n (%)	n (%)	n (%)	
[EPQ8Ar3] Product effectiveness: Impact on AK lesion clearance. (N=x)	n (%)	n (%)	n (%)	
[EPQ8Ar4] Product effectiveness: Amount of time it takes to start working. (N=x)	n (%)	n (%)	n (%)	
[EPQ8Ar5] Product side-effects: Amount of time it takes for local skin reactions to resolve. (N=x)	n (%)	n (%)	n (%)	
[EPQ8Ar6] Product side-effects: Number and type of local skin reactions. (N=x)	n (%)	n (%)	n (%)	
[EPQ8Ar7] Product side-effects: Severity of the local skin reactions. (N=x)	n (%)	n (%)	n (%)	
[EPQ8Ar8] Product tolerability: Ability to adhere to treatment dose, or intensity. (N=x)	n (%)	n (%)	n (%)	
[EPQ8Ar9] Other: (N=x) EPQ8Ar9oe	n (%)	n (%)	n (%)	

Note: Data from Clinician DCF, from week-24.

Table 2.44 Top-3 Factors Influencing Overall Clinician Satisfaction with Tirbanibulin at Week 24, If Retreated with Another Topical Treatment after Week 8

RS6 Among the list of factors that influenced your overall satisfaction with tirbanibulin (Klisyri®), please identify the three most important factors and rank them on a scale of importance from 1 to 3, where 1 is the first most important factor, 2 is the second most important factor and 3 is the third most important factor to you, by entering a number in the boxes next to only those factors in the following list.

Domain	Rank 1	Rank 2	Rank 3	Average Rank
[RS6Ar1]. Product convenience: Length of treatment, frequency, and easiness to take, etc. (N=x)	n (%)	n (%)	n (%)	
[RS6Ar2] Product effectiveness: Impact on skin appearance. (N=x)	n (%)	n (%)	n (%)	
[RS6Ar3] Product effectiveness: Impact on AK lesion clearance. (N=x)	n (%)	n (%)	n (%)	
[RS6Ar4] Product effectiveness: Amount of time it takes to start working. (N=x)	n (%)	n (%)	n (%)	
[RS6Ar5] Product side-effects: Amount of time it takes for local skin reactions to resolve. (N=x)	n (%)	n (%)	n (%)	
[RS6Ar6] Product side-effects: Number and type of local skin reactions. (N=x)	n (%)	n (%)	n (%)	
[RS6Ar7] Product side-effects: Severity of the local skin reactions. (N=x)	n (%)	n (%)	n (%)	
[RS6Ar8] Product tolerability: Ability to adhere to treatment dose, or intensity. (N=x)	n (%)	n (%)	n (%)	
[RS6Ar9] Other: (N=x) RS6Ar9oe	n (%)	n (%)	n (%)	

Note: Data from Clinician DCF, from week-24.

Table 2.45 Unscheduled Patient Encounters Reported at Week 24, If Retreated after Week 8

Domain	Week-24				Total (N=X)
	Retreated with Klisyri (RMH2Ar1) (N=x)	Retreated with Another Topical Treatment (RMH2Ar2) (N=x)	Retreated with Non- Topical Treatment (RMH2Ar3) (N=X)		
[US1_1r1] Number of unscheduled in-person clinic visits:	n (%)	n (%)	n (%)	n (%)	n (%)
[US1_1r2] Number of unscheduled tele-health visits:	n (%)	n (%)	n (%)	n (%)	n (%)
[US1_1r3] Number of unscheduled phone calls:	n (%)	n (%)	n (%)	n (%)	n (%)

